# Remote Limb Ischemic Conditioning to Enhance Muscle Power, Dynamic Balance, and Walking Performance in Children with Cerebral Palsy

Study Objectives	
The objective of this research study is to determine if remote limb ischemic conditioning (RLIC) can enhance quadriceps muscle power, dynamic balance and walking performance in children with cerebral palsy (CP).

Background & Rationale	
Ischemic conditioning is an endogenous phenomenon in which exposing a target organ or tissue to one or more brief episodes of ischemia results in protection of that organ against subsequent ischemia. The effects of ischemic conditioning are not confined within an organ but can be transferred from one organ to another, a technique called remote ischemic conditioning. A clinically feasible method for this is remote limb ischemic conditioning (RLIC), where episodes of ischemia and perfusion are induced with a blood pressure cuff placed on the arm.
 
In humans, the cardioprotective effects of RLIC have been demonstrated. For example, applying an inflated blood pressure cuff to the upper or lower limb has shown efficacy for protection in people undergoing cardiac surgeries, elective surgery to repair abdominal aortic aneurysm, experiencing myocardial infarction, and with symptomatic intracranial arterial stenosis. Subsequent studies have shown RLIC as neuroprotective and improves exercise performance in healthy young adults. Based on the promising results of our clinical trials which demonstrated that when paired with training, RLIC improves muscle strength and motor learning in healthy young and older adults respectively. Therefore, we postulate that the effects of RLIC might extend in neurological population such as CP.
 
Our central hypothesis is that the multifactorial mechanisms of RLIC can be harnessed as a neurorecovery agent to enhance rehabilitation and outcomes in children with CP. This research will focus on improving quadriceps power and dynamic balance since quadriceps weakness and impaired balance performance are often cited as major factors that limit the mobility and walking performance of children with CP. The results of our randomized controlled trials have shown that RLIC facilitates motor learning and muscle strength, and retention of these changes in older and young, neurologically intact adults. However, these learning and strength effects have only been seen only in healthy population. Hence, the next step is to investigate if RLIC can enhance performance of an ecologically valid motor task such as dynamic balance task, increase skeletal muscle power, and increase walking performance in children with CP.

	This study is important because if eventually effective, RLIC could have profound effect on the rehabilitation and recovery of brain plasticity and muscle performance in children with CP and other neurological population.
Study Design	Between groups repeated measures design.
Groups	
Group 1: Children with CP receiving RLIC
 
Group 2: Children with CP receiving sham conditioning
 
Children who qualify and consent will be randomly assigned to either group 1 or 2. Participants will be blinded to the group assignment and the assessor will be blinded to the participant's group assignment.

Number of Subjects & Power Analysis	
Sample size estimates are based on peak knee extension power data from Moreau et al. A total of 24 participants (12 in each group) will provide 80% power to detect an effect size of 0.62 at significance level of 0.05.
 
The sample size was calculated based on a two-sided Wald test of regression coefficients in linear mixed effects model adjusting for design effect and correlation of repeated measures from the same subjects.

Inclusion & Exclusion Criteria	
Inclusion Criteria:
 
 
1. Children diagnosed with unilateral or diplegic CP
 
2. Gross Motor Function Classification System (GMFCS) levels I-III
 
3. 6-13 years of age
 
 
Exclusion Criteria:
 
 
1. Children with other developmental disabilities such as autism, developmental coordination disorders, etc.
 
2. Children with cognitive deficits or communication problem
 
3. Children with balance disorders such as vestibular disorders, posterior fossa tumor etc.
 
4. Children with known cardiorespiratory dysfunctions
 
5. Children who are receiving other adjunct therapies such as TMS, tDCS, vagal nerve stimulation etc.
 
6. Presence of lower extremity condition, injury, or surgery which could compromise conditioning and training
 
7. Children with sickle cell disease
 

RLIC and Sham Conditioning	Remote limb ischemic conditioning will be achieved via blood pressure cuff inflation to 20 mmHg above resting systolic blood pressure up to 200 mmHg.  Sham conditioning will be achieved via blood pressure cuff inflation to 25 mmHg on the more involved thigh. Conditioning will involve 5 cycles of 5 minutes blood pressure cuff inflation followed by alternating 5 minutes of cuff deflation. Subjects will be blinded to their group assignment (RLIC or sham conditioning). Conditioning requires 45 minutes. RLIC or sham conditioning will be performed on visits 1-14.

Behavioral Training	
Three tasks will be used for behavioral training on visits 3-14.
 
 
1) Power training task (20-30 minutes)
 
2) Balance training task (15 minutes; rest breaks as needed)
 
3) Treadmill training (15 minutes)
 
 
Power Training: Prior to training and at the beginning of each training week, we will obtain 1 repetition maximum (1 RM) on each leg. 60-80% of the 1 RM will be used as training intensity with progression toward 80% based on that week's 1 RM. Training will involve unilateral and bilateral leg presses (Total Gym GTS, San Diego, CA), 3 times/week for 4 consecutive weeks (12 sessions). Each session will begin with 5 minutes of warm-up exercises. Each participant will perform 6 sets of 5-7 concentric extension contractions with maximum efforts, and with one-three minutes rest after each set.
 
Balance Task: The balance task requires subjects to stand on a movable platform (Stability Platform, model 16030L, Lafayette Instrument) and to keep the platform in a balanced, horizontal position. This task was selected because it can be easily modified to the appropriate level of difficulty in accordance with each subject's motor abilities.
 
Treadmill Training: We will use short burst interval treadmill training. We will use the self-selected and fast walking speeds determined by the 10-meter walk test as the training intensity for the child for each session. Short burst interval training will consist of 30 seconds fast followed by 30 seconds of slow walking. We chose this type of training since it closely resembles the walking performance of a child in the community.

Descriptive measures	
Demographic information, including age, dominant side, gender, ethnicity, race, level of physical activity, height, body weight, school grade, GMFCS level, prenatal, natal, or postnatal history, co-morbidities, current medications, history of any surgery, and current and past rehabilitation will be collected on all subjects on visit 1. Performing all these descriptive measures on visit 1 will allow us to determine the inclusion/exclusion of the participant in the study.

Outcome Measures	
The outcomes measured include-
 
Performance on:
 
 
1. Quadriceps power
 
2. Electromyography
 
3. Balance
 
4. Walking
 

	
Quadriceps power: will be measured using Humac Norm Isokinetic testing device (Computer Sports Medicine Inc, Stoughton, MA). Quadriceps power over 5 maximal test repetitions at 90°/sec will then be calculated every 10 ms (velocity x torque).
 
Electromyography (EMG): The EMG data will be used to quantify the electrical amplitude of quadriceps muscle. Increase in the amplitude of EMG is an indicator of neurophysiological adaptation to strength training. We will simultaneously record the EMG activity of quadriceps muscle while performing isokinetic testing. EMG data will be gathered 6-channel EMG system (Delsys Inc, USA) with the sampling frequency set at 1000 Hz. Surface EMG sensors will be placed at the muscle belly in the direction of muscle fibers, according to surface EMG for non-invasive assessment of muscles (SENIAM) guidelines (http://www.seniam.org). EMG data will be processed off-line in MATLAB R2016a (MathWorks, Natick, MA) with custom-written software using cutoff frequencies of 20 and 500 Hz for lower and upper band-pass, respectively and by averaging by averaging the amplitude of the EMG activation during the middle 3000 ms for each trial.
 
Performance on the standing balance task will be quantified by identifying the number of seconds in a 30-second trial that an individual is able to maintain the platform within <math>\pm 5^\circ</math> of horizontal.
 
Walking Performance:
 
Walking performance will be measured with:
 
 
1. Walking speed: Self-selected and fast walking speeds will be measured using 10-meter walk test. Children will complete three trials at each speed and the average of the respective trials will be considered for analysis. During these tests, children will walk across a GaitRITE digital mat (CIR Systems, Sparta, NJ) and we will quantify walking speed, step length, step width, and cadence.
 
2. Gait analysis: Lower extremity walking kinetics and kinematics will be measured using a 10-camera motion analysis system (Qualisys Inc., Gothenburg, Sweden) sampling at 200 Hz. Specific kinematic variables are hip, knee, and ankle joint angles at midstance, peak hip extension, peak knee extension, and peak ankle plantarflexion during stance phase. Kinetic dependent variables include peak hip, knee, and ankle sagittal plane joint moments and total support moment, and peak positive and negative hip, knee, and ankle sagittal plane joint power.
 
3. Accelerometry: Lower extremity activity will be measured using accelerometers worn on bilateral ankles for 24 hours. Specific accelerometry variable will be number of steps.
 

--	---

Order of Experiment/Study Visits	
This study involves 16 total visits. Participants will be in the study for up to 8 weeks. Please refer to Table 1 for a timeline of study visits.
 
Visit 1: We will provide informed consent and assent and gather demographic data. Next we will perform baseline assessments for the performance on the quadriceps power, EMG, balance, and walking.
 
Then, we will quantify power of bilateral knee extensor by recording peak knee extensors torque and electromyography of bilateral rectus femoris, vastus lateralis, and vastus medialis.
 
Next, we will gather measurements on balance task.
 
Next, we will assess walking performance using 10-meter walk test, 3-D gait analysis, and accelerometry.
 
Subjects will then be randomized to their treatment group. After randomization, subjects will undergo RLIC or sham conditioning (see RLIC and Sham Conditioning for the details). This visit will take approximately: 3 hours.
 
Visit 2: Subjects will undergo RLIC or sham conditioning This visit will take approximately: 1 hour.
 
Visit 3-14: Subjects will undergo RLIC or sham conditioning. Next, behavioral training will commence (power training task and balance training). The order of behavioral training task practice will be randomized. Visits 3-14 will occur every alternate business day. These visits will take approximately: 2-2.5 hours.
 
Visit 15: Subjects will complete post-testing which will include a) quadriceps power; b) EMG; c) balance task, and d) walking performance. Visit 15 will be on the next business day after visit 14. During this visit, participants will not receive RLIC or sham conditioning. This visit will take approximately: 2 hours.
 
Visit 16: Post-test performance assessment on power, EMG, balance, and walking will be performed after 4-weeks from the visit 15. Participants will not receive RLIC or sham conditioning during the follow-up visits. Participants will fill out a survey on the follow-up visit indicating whether they think that they received RLIC or sham treatment. This visit will take approximately: 2 hour.

Data Analysis	
Data will be analyzed using a mixed model ANOVA with time (pretest, posttest, and follow-up) as within subject factor and group (RLIC vs. sham treatment) as between subject factor.

Safety Considerations & Monitoring	
The risks of participating in the rehabilitation intervention are minimal and are similar to the risks encountered during routine physical and occupational therapy services.
 
Conditioning:

	
The likely risks are:
 
 
1. Bruising on the conditioning thigh: To avoid bruising from the pressure cuff, participant's arm will be covered with a folded cotton pillowcase.
 
2. Discomfort: To avoid discomfort in the conditioning thigh during each conditioning cycle, we will ask the participant about discomfort. If the participant reports discomfort, we will reposition the pressure cuff on the thigh and allow the participant to move the thigh during 5-minutes of deflation cycle.
 
3. Pain or tingling on the conditioning arm: To avoid pain or tingling in the conditioning thigh during the conditioning cycle, we will ask the participant about pain and tingling. If the participant reports pain or tingling, we will reposition the pressure cuff on the thigh and allow the participant to move the thigh during 5-minutes of deflation cycle.
 
 
Power Training:
 
The likely risks are
 
 
1. Knee or thigh pain: To avoid the knee or thigh pain, participants will perform warm-up exercises for 5 minutes before starting the strengthening.
 
2. Muscle fatigue and delayed onset muscle soreness: Power training on every alternate day will allow sufficient time to recover from muscle fatigue and delayed onset muscle soreness.
 
 
Balance:
 
The less likely risks are
 
 
1. Falling from the balance board: To avoid falling from the balance board, participants will be permitted to use a handrail as needed for safety during balance task and up to two research team members will supervise the balance performance. Participants will also wear a gait belt for safety, which will help the research team member to catch the participant if they start to fall.
 
 
Treadmill:
 
The less likely risks are
 
 
1. Muscle fatigue and falling from the treadmill: To avoid falling from the treadmill, participants will be provided sufficient rest. Participants will also be allowed to use a handrail as needed and will also wear a gait belt for safety.
 
 
In order to monitor for further overall safety, we will continuously monitor lightheadedness, respiratory distress, cyanosis, and spasms. We will record and monitor heart rate, blood pressure, and oxygen saturation before, during, and after each session of RLIC. Sessions will be terminated if heart rate <60 bpm or >160 bpm, systolic BP <70 mmHg or >130mmHg, diastolic

--	--

	BP <40 or >90 mmHg, O 2 saturation <90%, or if pain is >6 on 10-point Likert pain scale. Moreover, during the follow up session, all subjects will be asked questions about any adverse effects that resulted from participation in this study.
Investigators	PI: [name], PT
Number of Centers	1 center: East Carolina University
Key References	Please see the reference list.

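### Functional level (GMFCS I-III) is recorded before randomisation but used in neither allocation nor analysis, at a cost in precision and interpretability in a trial of 24 children

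*Combined protocol and SAP*

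**What the plan says.** All references are to the combined protocol and SAP.

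- **Allocation.** The Groups section says "Children who qualify and consent will be randomly assigned to either group 1 or 2". Under Order of Experiment/Study Visits, the Visit 1 entry places this step after baseline testing: "Subjects will then be randomized to their treatment group". Neither place gives a ratio, sequence method, blocks, strata, minimisation or concealment.
- **Eligibility.** The Inclusion Criteria accept "Gross Motor Function Classification System (GMFCS) levels I-III", unilateral or diplegic CP, and ages 6 to 13.
- **Sample size.** The power statement gives "A total of 24 participants (12 in each group"), which "will provide 80% power to detect an effect size of 0.62" "at significance level of 0.05", from a "two-sided Wald test of regression coefficients in linear mixed effects model". The figure of 12 per group appears only here, as a target and not as an allocation rule.
- **Data available.** Descriptive measures, collected at Visit 1 and used to decide eligibility, include "GMFCS level, prenatal, natal, or postnatal history, co-morbidities, current medications".
- **Analysis.** Data Analysis names a mixed-model ANOVA with time (pretest, posttest, follow-up) within subjects and group between subjects. It has no term for GMFCS level, CP type or age.

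**The concern.** GMFCS grades gross motor function, so it can be expected to relate to power, balance and walking scores. Because each child has a pretest, the group-by-time comparison cancels a stable difference in level between the arms. It does not cancel a difference in how much children at different levels gain from four weeks of training.

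The protocol gives some reason to think that gains could differ. The balance outcome is seconds achieved within a 30-second trial, so a child who starts high has less room to improve. If gains do differ by level, an uneven split of GMFCS classes moves the group contrast by chance in one direction or the other, and nothing in the plan limits or adjusts for it. Variation in gain between classes also stays in the error term, where a model term could remove it.

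With 12 children per arm, a split that readers would question is not rare, and the team would have no pre-specified adjustment to offer.

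**Working it through.** **1. The plan's own figure.** Inputs from the power statement: 24 children, effect size 0.62, two-sided 0.05, 80% power. A plain two-sample comparison needs 2 × (1.960 + 0.842)² / 0.62² = 2 × 7.85 / 0.3844 = 40.8, so 41 per arm. Twelve per arm therefore depends on the repeated-measures correlation and design effect, for which no values are given, or on another meaning of 0.62. The figure cannot be reproduced from the text. Whether 24 is right is a separate question. Below, 80% at 12:12 is taken as stated.

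**2. Balance on functional level with 12:12 fixed.** Let K be the number of children in one GMFCS class (assumed) and x the number of them in one arm. Then

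P(x) = C(K, x) × C(24 − K, 12 − x) / C(24, 12), with C(24, 12) = 2,704,156.

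The gap between arms is |2x − K|. For K = 8, a gap of 4 or more means 6:2, 7:1 or 8:0. The counts are 224,224 + 34,944 + 1,820 = 260,988. Doubled for either direction this is 521,976, and 521,976 / 2,704,156 = 19.3%. In one named direction it is half that, about 9.7%.

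| K | P(gap of 4 or more) |
|---|---|
| 2 or 3 | 0 |
| 4 | 9.3% |
| 5 | 3.7% |
| 6 | 15.5% |
| 7 | 6.9% |
| 8 | 19.3% |
| 9 | 8.9% |
| 10 | 21.4% |
| 11 | 10.0% |
| 12 | 22.0% |

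Odd K gives lower values because only odd gaps are possible, so the smallest gap counted is 5.

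**3. What such a split does.** At 6:2, the class makes up 6/12 of one arm and 2/12 of the other, a difference of 1/3. If mean gain differs by g between classes, the contrast in change shifts by g/3 in that realised allocation. The documents give no value for g.

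**4. Arm sizes, if allocation were simple 1:1.** P(12:12) = 2,704,156 / 2²⁴ = 16.1%, and P(10:14 or more unequal) = 54.1%. Scaling from 80% at 12:12, power at a:b is Φ(2.802 × √(ab/144) − 1.960):

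- 11:13: 79.7%
- 10:14: 2.802 × √(140/144) − 1.960 = 0.80, so 78.9%
- 9:15: 77.4%
- 8:16: 2.802 × √(128/144) − 1.960 = 0.68, so 75.2%
- average over all splits: 78.2%

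**5. With stratified blocks of 2 and 4.** An unfinished block leaves a gap of at most 2 in a stratum, so a gap of 4 within a stratified class cannot arise at randomisation. Over two strata the largest overall gap is 2 + 2 = 4, that is 10:14, with power of 78.9%.

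**The case against.** The best defence is that randomisation already does its job. Chance imbalance is part of what the standard error and the 5% level allow for, so omitting a stratum invalidates nothing. Training is also scaled to the child: the power load is a percentage of that week's one-repetition maximum, the balance task is adjusted to ability, and treadmill speeds come from the child's own walk test. The GMFCS mix is unknown, and if few level III children enrol, a I-II versus III stratum does little. Nor do the documents show that GMFCS is a better single factor than age or CP type.

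Much of this stands. The test is valid, and individual scaling weakens the case for unequal gains, though it does not establish equal ones. The choice of GMFCS is a judgement: it is the recorded item that grades motor function directly. Two classes of each of the three factors would make 8 cells, an average of 3 children each.

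Four stronger readings are tempting, and the documents do not support them:

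- *That the trial uses simple randomisation.* The method is not stated. The arm-size probabilities show what the text permits, not what is planned.
- *That unequal arms seriously threaten power.* A 10:14 split costs about 1 percentage point and 8:16 about 5.
- *That imbalance biases the result by an amount comparable with the planned effect.* Assuming g of 0.5 to 1.0 SD, a 6:2 split shifts the contrast by 0.17 to 0.33 SD. But that g is not in the documents, the shift is chance error and not bias, and the type of the 0.62 effect size is not stated, so the two may not share a scale.
- *That stratified blocks guarantee 12 per arm.* They do not (step 5).

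**Conclusion.** The point holds as one of precision and interpretability, not validity. A characteristic likely to matter for the outcomes is known before randomisation and used nowhere. With 12:12 fixed, the chance that the arms differ by four or more children of one GMFCS class is 15.5% to 22.0% when the class has an even number of children from 6 to 12, and 7% to 10% when it has 7, 9 or 11. It is lower for smaller classes.

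These figures rest on an assumed GMFCS mix. Whether such a gap alters the result depends on a difference in gain between classes that the documents neither give nor exclude. Protecting 12 per arm is a minor matter, worth about 2 points of average power at most plausible reading (80% to 78.2% under simple allocation). The change is worth making because it is cheap and uses data already collected.

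**What to change.** Replace the allocation sentence with:

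> Children will be randomised 1:1 by concealed permuted blocks of small varying size (2 and 4), stratified by GMFCS level in two classes (I-II versus III, or I versus II-III if few level III children are expected), as recorded at Visit 1 before randomisation.

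Choose the class boundary before the list is made. In Data Analysis, add the GMFCS stratum and its interaction with time as fixed terms. The interaction is the term that deals with a difference in gain. If enrolment has begun, the model terms can still be pre-specified before unblinding.

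**Cost.** A new allocation list and one analysis sentence, with no extra children, visits or measurements. With complete data on 24 children at three times, the stratum takes one between-child degree of freedom (22 to 21) and its interaction takes two within-child degrees of freedom (22 × 2 = 44 to 21 × 2 = 42). Each stratum may end with an incomplete block, so the arms could still finish as unequal as 10:14. Levels merged within one class, CP type and age remain unbalanced by design.

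### The 3000 ms EMG averaging window is longer than any knee extension at 90°/sec, and the plan does not say what an EMG trial is, so a continuous window averages in return or rest.

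*Combined protocol and SAP*

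**What the plan says.** Under Outcome Measures, the quadriceps power entry gives the test: "Quadriceps power over 5 maximal test repetitions at 90°/sec will then be calculated every 10 ms (velocity x torque". The EMG entry ties the EMG recording to that test: "We will simultaneously record the EMG activity of quadriceps muscle while performing isokinetic testing". It then reduces the signal off-line, after band-pass filtering, by "averaging the amplitude of the EMG activation during the middle 3000 ms for each trial".

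The same section gives *trial* a meaning for two other measures. For balance the score comes from "identifying the number of seconds in a 30-second trial"; for walking speed, "Children will complete three trials at each speed and the average of the respective trials will be considered for analysis". There is no counterpart for EMG. The documents give no range of motion, return speed, pause between repetitions or onset/offset rule, and they describe neither an isometric hold nor a step that isolates the extension phase. The visit 1 description pairs EMG with knee extensor torque and adds no separate contraction.

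EMG is one of four listed outcomes. The plan says how a rise will be read: "Increase in the amplitude of EMG is an indicator of neurophysiological adaptation to strength training". The Data Analysis section specifies a "mixed model ANOVA with time (pretest, posttest, and follow-up) as within subject factor", with treatment group as the between-subject factor.

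**The concern.** A stated processing number does not fit the stated test. A window of 3000 ms would suit a sustained contraction, but the only contraction described is a moving one at 90°/sec, which is over well before 3 s. A continuous window therefore takes in time when the quadriceps is not extending the knee.

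The averaged amplitude then reflects two things: how strongly the muscle is activated in extension, and how much of the window is extension. The second depends on range of motion, return pace and pauses, none of which the plan fixes. If a child's timing differs between visits 1, 15 and 16, the EMG value can change while extension-phase activation has not, and the plan would read a rise as neurophysiological adaptation. Two analysts following the text could also obtain different values from one recording. With 24 children, avoidable noise in an outcome is worth removing.

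**Working it through.** The 3000 ms is a processing rule with no derivation in the plan, so there is no figure to reproduce. The check is kinematic.

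**Inputs from the documents:** speed 90°/sec; 5 repetitions; window 3.0 s.

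**Assumed, because the documents do not give them:** arc 60-120 degrees; return speed 90-300°/sec; pause after each return 0-1 s; the set may end on the last extension, return or pause.

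**1. Arc covered by the window.** 3.0 s × 90°/sec = 270 degrees. This needs no assumption about range of motion beyond the knee's arc being smaller than 270 degrees.

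**2. Duration of one extension = arc / 90.** The largest possible extension share of the window is that duration divided by 3.0.

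| Arc | One extension | Largest extension share | Smallest return/rest share |
|---|---|---|---|
| 60° | 0.67 s | 0.22 | 78% |
| 90° | 1.00 s | 0.33 | 67% |
| 120° | 1.33 s | 0.44 | 56% |

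So if a trial is one repetition, at least 56-78% of a continuous window is not extension.

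**3. If a trial is the five-repetition set.** One cycle lasts arc/90 + arc/return speed + pause. The window is the central 3.0 s of the set. The shortest set in the grid is 4 × (0.667 + 0.2) + 0.667 = 4.13 s, so the window always fits. The grid has 61 arcs × 22 return speeds × 11 pauses × 3 end-points = 44,286 settings. The non-extension share runs from 0.167 to 0.778:

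- *Low end* (75°, 300°/sec return, no pause, ends on extension): cycle 0.833 + 0.25 = 1.083 s; set 4 × 1.083 + 0.833 = 5.167 s; window 1.083 to 4.083 s. It holds exactly three extensions: 3 × 0.833 / 3.0 = 0.833 extension, 0.167 not.
- *High end* (60°, 90°/sec return, 0.5 s pause, ends on extension): cycle 1.833 s; set 8.0 s; window 2.5 to 5.5 s. It holds only the third extension: 0.667 / 3.0 = 0.222 extension, 0.778 not.

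**4. If extension phases are cut out and joined first.** Five extensions last 5 × arc/90 = 3.33 s (60°) to 6.67 s (120°). A 3.0 s window then fits and contains extension only. The plan does not describe this step.

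**5. How far timing alone can move the value.** Let *s* be the extension share and *q* the return/pause amplitude relative to a constant extension amplitude. The window mean is *s* + *q*(1 − *s*). Shorten the pause from 0.5 to 0.25 s and change nothing else:

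- *No effect* (90°, 90°/sec return, ends on extension): with the 0.5 s pause the set is 11.0 s and the window 4.0 to 7.0 s; with 0.25 s the set is 10.0 s and the window 3.5 to 6.5 s. Each holds one 1.0 s extension, so *s* = 0.333 both times and the change is 0%.
- *Intermediate* (90°, 180°/sec return, ends on return): *s* goes from 0.417 to 0.500. With *q* = 0.1 the mean goes from 0.475 to 0.550, a rise of 15.8%; with *q* = 0.5 the rise is 5.9%.
- *Largest in the grid* (60°, 90°/sec return, ends on extension): with the 0.25 s pause the set is 7.0 s and the window 2.0 to 5.0 s. It holds the third extension and 0.25 s of each neighbour, so *s* goes from 0.222 to (0.667 + 0.5)/3.0 = 0.389. With *q* = 0.1 the mean goes from 0.30 to 0.45, a rise of 50%. With *q* = 0.5 it goes from 0.611 to 0.694, a rise of about 14%.

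**The case against.** The strongest reply is that the text is ambiguous rather than wrong. *Continuous* is not the plan's word; custom software might detect active segments and take the middle of those, and step 4 shows that 3000 ms would then fit. The documents do not exclude this, so mixing is a consequence of the plain reading and not proof of what the laboratory will do. But no such step is described, and someone applying the rule as written would average in return or rest.

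Second, the size of the effect rests wholly on assumed timing, and some permitted settings give none. That stands: the range must include zero, and nothing in the documents shows that timing will differ between visits.

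Third, a reader might infer that the window is also at fault because it drops extension time; for any arc above 54 degrees (54/90 × 5 = 3.0 s) it cannot hold all five extensions. The documents do not support treating that as a harm. Taking the middle part is a deliberate trim, and a mean amplitude is not biased by it unless amplitude varies systematically across or within repetitions, for which they give no evidence.

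Fourth, a reader might infer that the treatment comparison is biased or the trial underpowered as a result. Neither follows. The rule is the same in both arms, and the plan states "Sample size estimates are based on peak knee extension power data", not EMG.

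Finally, the EMG and dynamometer systems are separate devices. Simultaneous recording is stated, but a shared trigger or clock is not, so alignment cannot be taken for granted.

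**Conclusion.** The point holds for a continuous window. That such a window cannot fit inside one extension follows from the plan's own numbers. The share of return or rest, at least 56-78% for one repetition or 17-78% for the set, rests on the assumed arcs, return speeds and pauses. The effect of a timing change on the EMG value is conditional: for a pause shortened from 0.5 to 0.25 s it is 0 to about 50% over the assumed grid when return/pause amplitude is 10% of extension amplitude, and smaller when that amplitude is higher.

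What is at stake is noise and time effects that are hard to interpret in one of four listed outcomes. This should be fixed before analysis. Confidence is high in the mismatch between window and test, but not in any particular size of effect.

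**What to change.** Replace the 3000 ms rule with a per-repetition measure:

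- Identify the extension phase of each repetition from the simultaneously recorded dynamometer signal, or from EMG onset and offset if the two systems are not time-aligned.
- Compute EMG amplitude over that phase and average across the 5 repetitions.
- State what a trial means for EMG, and apply the same rule at visits 1, 15 and 16.

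The cost is a change to the off-line processing code, fixed before analysis, plus confirming that the EMG and dynamometer recordings can be aligned in time. The power calculation already needs velocity every 10 ms, so no child needs extra testing.
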